## 10.2 SECONDARY ANALYSIS

### Superiority test of Bim SR 15 µg versus SLT

As the secondary efficacy analysis, a superiority test of Bim SR 15 µg versus SLT will be performed if noninferiority is demonstrated in the primary efficacy analysis. Superiority of Bim SR versus SLT is considered achieved if the upper limit of the 95% CI is < 0 mm Hg at Weeks 4, 12, and 24. The mITT population will be used.

### Time to initial use of non-study IOP-lowering treatment (as determined by the investigator)

Time to the event of the initial use of non-study IOP-lowering treatment from the Date of the First Treatment will be estimated using Kaplan-Meier (KM) method with graphical displays.

Time to initial use of non-study IOP-lowering treatment = (Date of initial use of non-study IOP-lowering treatment – Date of the First Treatment) +1,

where the Date of the First Treatment for SLT is the SLT Treatment date (study Day 1), and the Date of First Treatment for Bim SR is Bim SR Cycle 1 Day 1 administration date (study Day 4).

Additionally, for Bim SR, the time to non-study IOP-lowering treatment from the second injection and the time to non-study IOP-lowering treatment from the third injection will be summarized:

Time to initial use of non-study IOP-lowering treatment from the second Bim SR implant = (Date of initial use of non-study IOP-lowering treatment after the second Bim SR implant – Date of the second Bim SR implant) +1

Time to initial use of non-study IOP-lowering treatment from the third Bim SR treatment = (Date of initial use of non-study IOP after the third Bim SR implant -lowering treatment – Date of the third Bim SR implant) +1

In the calculation of time to initial use of non-study IOP-lowering treatment, if a patient did not use any non-study IOP-lowering medications in an eye, then the event (initial use of non-study IOP-lowering treatment) time will be censored at the study exit date or the last visit date if the study exit date is not available.

In the calculation for the time to the event of non-study IOP-lowering treatment from the second Bim SR implant, patients with at least two Bim SR implants will be used, and the event will be censored at the third Bim SR implant if the patients didn't use any non-study IOP-lowering medications up-to the third implant.

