4.5.2 Prohibited Medications/Treatments

The decision to administer a prohibited medication/treatment is taken with the safety of the study participant as the primary consideration. When possible, Allergan should be notified before the prohibited medication/treatment is administered.

During the study, patients must not participate in other investigational drug or device studies.

Nonstudy IOP-lowering Treatments

Any concurrent nonstudy IOP-lowering treatment (eg, topical ophthalmic medication containing an ocular antihypertensive, LT) is prohibited in either eye during the study (through Week 52), unless necessary for the safety of the patient due to inadequate control of IOP as determined by the investigator. Inadequate control of IOP should be confirmed at a subsequent visit (scheduled or unscheduled visit). Initiation of treatment in one eye should not automatically lead to initiation of treatment in the contralateral eye. Each eye should be evaluated on an individual basis when determining the need for additional nonstudy IOP-lowering treatments. If nonstudy IOP-lowering treatment is initiated, the investigator will be expected to attest to the need for additional nonstudy IOP-lowering treatment for safety reasons for each eye individually. Use of any concurrent nonstudy IOP-lowering treatment with any known effect on study outcomes (eg, crossover effect on the contralateral eye) is prohibited during the study.

In order to maintain patient masking to treatments assigned to each eye, patients who have received nonstudy topical IOP-lowering treatment in a Bimatoprost SR eye will receive Sham Bimatoprost SR administration in that eye on the Bimatoprost SR Cycle 2 (and Cycle 3 for Stage 1 patients) administration day(s). If nonstudy topical IOP-lowering medication is initiated in an SLT eye, the patient will continue to receive Sham Bimatoprost SR administration in the SLT eye on the administration day(s). In all cases, the contralateral eye that does not require nonstudy topical IOP-lowering medication will maintain the same

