7.2 Collection and Derivation of Primary and Secondary Efficacy Assessments

The primary efficacy measurement is IOP, which will be measured in each eye using the Goldmann applanation tonometer. Two consecutive measurements will be taken for each eye. If these 2 measurements differ by > 1 mm Hg, then a third measurement will be performed. If the first 2 measurements differ by ≤ 1 mm Hg, or a third measurement is required but only 2 measurements are obtained, then the IOP value for a given eye is the average of the 2 measurements. If 3 measurements are required (ie, the first 2 measurements differ by > 1 mm Hg) and obtained, then the IOP value for the given eye is the median of the 3 measurements. If, for any reason, only a single measurement is obtained, then this measurement will be used as the IOP value.

To avoid confounding of efficacy data, IOP measurements obtained after initiating the use of nonstudy IOP-lowering medication in an eye will be included in the study database but will be excluded from efficacy analysis.

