Additionally, ANCOVA including within-subject correlation at each visit will be conducted using the observed values of ITT population, where IOP measurements obtained after initiating the use of non-study IOP-lowering medication will be set to missing. At each visit, the model for IOP change from baseline is specified as: IOP Change from Baseline = Treatment + Eye + Baseline IOP, where Eye is primary eye or contralateral eye. A compound symmetric covariance matrix will be used for between eye correlation.

The tipping-point sensitivity analysis will also be used to assess the robustness of the analysis results. A multiple imputation (MI) will be performed to the missing data as the first step; then different shifts using various assumptions on the missing IOP CFB will be applied to the imputed missing values in Bim SR treated eyes separately (note: shift will not be applied to SLT treated eyes); finally MMRM analyses will be conducted based on the imputed data with shifts and the corresponding tipping region of the shifts will be used to evaluate the robustness of the noninferiority conclusion.

In the MI procedures, a two-step method will be used to impute the missing values at Weeks 4, 8, 12, 15, 20, and 24 for each eye. During Step 1, missing intermittent data will be imputed to obtain a monotone missing pattern and during Step 2 linear regression will be used to impute the remaining missing values. Note that baseline IOP values associated with each eye must not be missing in any of the patients; otherwise they will be excluded from this analysis. At least twenty-five (25) sets of imputed datasets will be created using SAS proc MI procedure. A sample code is shown below for Hour 0 IOP measurements associated with each eye:

```
proc mi data=iop nimpute=25 seed=123451 out=_miint;  
  var baseline week4_hr0 week8_hr0 week12_hr0 week15_hr0 week20_hr0 week24_hr0;  
  by treatment;  
  mcmc chain=single impute=monotone;  
run;  
  
proc mi data=_miint nimpute=1 seed=123457 out=mifull;  
  class race_group sex lens;  
  var race_group sex lens age baseline week4_hr0 week8_hr0 week12_hr0 week15_hr0 week20_hr0  
  week24_hr0;  
  monotone regression (week4= race_group sex lens age baseline/details);  
  monotone regression (week8= race_group sex lens age baseline week4/details);  
  monotone regression (week12= race_group sex lens age baseline week4 week8/details);  
  monotone regression (week15= race_group sex lens age baseline week4 week8 week12/details);  

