## **16.0 DATA HANDLING CONVENTIONS**

### **16.1 EFFICACY DATA**

As stated in protocol [Section 5.9.1.5](#) Retreatment with Bim SR, when eye(s) received non-study IOP lowering medication or procedure, to avoid confounding of efficacy data, IOP measurements obtained after initiating the use of non-study IOP-lowering medication or procedure in an eye will be treated as missing for that eye.

Additionally, handling of missing data will be supplemented by sensitivity analyses using multiple imputation and tipping point (adding different penalties on the imputed values) approach.

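### The censoring rules for time to non-study IOP-lowering treatment (SAP 10.2) mention medications only, so an eye rescued by a procedure alone would, read literally, be censored although it had the event

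*SAP*

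**What the plan says.** The endpoint in SAP 10.2 is defined on treatment: "Time to the event of the initial use of non-study IOP-lowering treatment from the Date of the First Treatment". The protocol shows how wide that term is. Section 4.5.2 reads "Any concurrent nonstudy IOP-lowering treatment (eg, topical ophthalmic medication containing an ocular antihypertensive, LT) is prohibited in either eye", so laser trabeculoplasty counts as well as drops.

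The two censoring sentences in the same part of SAP 10.2 use a narrower word. For time from first treatment, an eye is censored at study exit (or at the last visit if there is no exit date) "if a patient did not use any non-study IOP-lowering medications in an eye". For time from the second implant, it is censored at the third implant "if the patients didn't use any non-study IOP-lowering medications up-to the third implant".

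The rules for pressure readings after rescue also differ in wording. SAP 16.1, the general convention for efficacy data, applies "when eye(s) received non-study IOP lowering medication or procedure" and treats later readings in that eye as missing. The ANCOVA text in SAP 10.4 says "IOP measurements obtained after initiating the use of non-study IOP-lowering medication will be set to missing". Protocol 7.2 excludes from efficacy analysis "IOP measurements obtained after initiating the use of nonstudy IOP-lowering medication in an eye".

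**The concern.** An event definition and its censoring rule should divide the eyes into two groups that do not overlap. Here they overlap. An eye that had laser trabeculoplasty and never used drops meets the definition of the event and also meets the stated condition for censoring. A programmer who follows the censoring sentence would carry that eye to study exit as event-free.

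This is not far-fetched in this population. Protocol 4.3 enrols patients whose topical therapy is failing for reasons such as intolerance or nonadherence, and requires that they be suitable candidates for SLT. Protocol 4.4 requires that they have had no earlier laser trabeculoplasty. A rescue by laser without drops is therefore plausible, though nothing in the documents says how often it happened. At stake is the accuracy of a secondary efficacy curve that readers will use to judge how long each treatment lasts.

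**Working it through.** **No plan figure to reproduce.** The plan states no rescue rate and no share of rescues by procedure. Its sample-size figures do not depend on the rescue rule. The check is therefore a comparison of texts, followed by an illustration on assumed rates.

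**Step 1: run each kind of eye through SAP 10.2.**

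| Rescue in the eye | Meets the event definition (treatment) | Meets the censoring condition (no medications) |
|---|---|---|
| None | No | Yes |
| Drops only | Yes | No |
| Procedure first, drops later | Yes, dated at the procedure | No |
| Procedure only | Yes | **Yes** |

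Only the last row conflicts. The problem is confined to eyes whose sole rescue was a procedure.

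**Step 2: ask whether medication is shorthand for both.** SAP 16.1 names medication and procedure side by side, and one passage of Protocol 4.5.2 likewise names medication and treatment as alternatives. SAP 8.4.2, under ocular medications, takes the identification of a non-study IOP-lowering medication from what the investigator enters on the eCRF. The SAP has no parallel rule for a rescue procedure. The shorthand reading is possible, but nothing in the documents states it.

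**Step 3: illustrate the size.** Let s be the true share of eyes rescued in an arm and f the fraction of those rescued by procedure only. Assume complete follow-up, so that the wrongly censored eyes leave at the same point as the eyes that were never rescued. Then

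- reported rescue = s × (1 − f)
- understatement = s × f

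| s (assumed) | f = 5% | f = 10% | f = 20% |
|---|---|---|---|
| 10% | 9.5% (0.5 points low) | 9.0% (1.0) | 8.0% (2.0) |
| 20% | 19.0% (1.0) | 18.0% (2.0) | 16.0% (4.0) |
| 30% | 28.5% (1.5) | 27.0% (3.0) | 24.0% (6.0) |

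The extremes are 0.10 × 0.05 = 0.005 and 0.30 × 0.20 = 0.06, which gives 0.5 to 6 percentage points. Both s and f are assumptions.

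**Step 4: trace the pressure readings.** SAP 10.1 has no rescue rule of its own for the primary MMRM. SAP 16.1 is headed as the convention for efficacy data, covers medication or procedure, and exempts no analysis. If it governs, post-procedure readings leave both the MMRM and the ANCOVA. SAP 10.4 and Protocol 7.2 are then narrower restatements of the same rule. What is missing is a sentence saying that 16.1 takes precedence. Its stated source does not help: it cites Protocol 5.9.1.5, whose current text contains no rule on readings after rescue.

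**The case against.** The best reply is that the sentence can be read sensibly. The section title and the event definition say treatment, and the first censoring sentence itself names the event in brackets as use of treatment. An eye given laser has a date of first treatment, so its event time is defined, and a censoring sentence is normally taken to cover eyes without the event. The protocol also uses the two words loosely: Sections 8.9 and 8.10 give essentially the same follow-up rule, one with medication and one with treatment. This stands as far as it goes. Censoring a procedure-only rescue is the literal effect of the sentence, not its only possible reading. But an SAP should not leave the choice to the programmer, and the documents do separate the two terms elsewhere.

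Procedure-only rescue may also be rare. Protocol 4.4 excludes patients with a foreseen need for eye surgery or laser, Protocol 4.3 requires that drops would suffice if used properly, and Protocol 4.5.2 lets patients who need incisional surgery leave early. That limits the likely size but does not remove the conflict.

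Two stronger readings are tempting. A reader might infer that the ANCOVA keeps readings lowered by a procedure. That follows only if SAP 10.4 is read without 16.1; being silent on procedures does not cancel the general rule. A reader might also infer that the error favours Bimatoprost SR, because that eye has had no laser while the SLT eye has, and Protocol 1.1 calls repeat laser trabeculoplasty controversial. The documents give no count of procedures by arm, so the direction is conjecture.

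**Conclusion.** The point holds for the two censoring sentences in SAP 10.2: followed as written, they censor an eye that had the event by the endpoint's own definition. The consequence would be an understated rescue rate in whichever arm had procedure-only rescues. The documents do not allow an estimate. The range of 0.5 to 6 percentage points rests wholly on assumed rates (10% to 30% of eyes rescued, 5% to 20% of those by procedure only) and on complete follow-up.

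The stakes are modest. The visible text of SAP 10.2 plans Kaplan-Meier estimates and graphs for this endpoint, with no test or decision rule. The noninferiority decision in SAP 10.1 uses the MMRM, which excludes post-procedure readings if SAP 16.1 governs; the same holds for the ANCOVA. For those two analyses the need is alignment of wording, not correction of a shown error.

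**What to change.** 1. In both censoring rules of SAP 10.2, replace medications with *treatment (medication or procedure) in that eye*.
2. State that the event date is derived from both the concomitant medication and the concomitant procedure records, and name the fields that identify an IOP-lowering procedure by eye.
3. In SAP 10.4, give the ANCOVA sentence the scope of SAP 16.1.
4. Add one sentence to SAP 16.1 saying that its rule (medication or procedure, by eye) governs all efficacy analyses, including where Protocol 7.2 mentions medication only. Correct its cross-reference to Protocol 5.9.1.5 at the same time.

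The cost is SAP wording plus one derivation rule, with no new visits or assessments. A protocol amendment is not needed. One item needs checking first. Concomitant procedures are collected throughout the study, but the documents do not show that they are flagged by eye or as IOP-lowering. If they are not, someone masked to treatment would need to classify the recorded procedures before the lock.

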**Percentage of Bim SR and SLT eyes achieving  $\geq 20\%$  reduction by visit**

[figure not shown]
Number and percent of Bim SR and SLT eyes that have achieved a  $\geq 20\%$  reduction in IOP by each post-baseline visit in each eye will be summarized.

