8.9 Early Discontinuation of Patients

Patients may voluntarily withdraw from the study at any time.

Patients who have received nonstudy IOP-lowering medication in one or both eyes, or who do not undergo Cycle 2 (or Cycle 3, for Stage 1 patients) administration, will be followed for the duration of the study through the Week 52/Exit visit.

If the implant has been removed, the patient may discontinue the study if based on investigator assessment the eye is in stable condition, at which time they should complete the Week 52/Exit visit procedures.

Notification of early patient discontinuation from the study and the reason for discontinuation will be made to Allergan and will be clearly documented on the appropriate case report form.

When patients discontinue before Week 52/Exit, the site should complete all procedures for the Week 52/Exit visit at the patient's last visit.

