## 4.0 INTRODUCTION

This statistical analysis plan (SAP) provides a more technical and detailed elaboration of the statistical analyses of the efficacy and safety data as outlined and/or specified in the Study Protocol 192024-095 ([Amendment 3](#)). Specifications of tables, figures, and data listings (TFLs) are contained in a separate document. Additionally, if data are to be excluded from per-protocol analyses, a separate document will provide detailed rules for the data exclusion.

Study 192024-095 is a multicenter, paired-eye, randomized, efficacy evaluator-masked 14-month study conducted in 2 stages (Stage 1 and 2). The safety and intraocular pressure (IOP)-lowering effect of Bimatoprost SR (Bim SR) will be compared with selective laser trabeculoplasty (SLT) in open-angle glaucoma (OAG) or ocular hypertension (OHT) patients who are not adequately managed with topical medication for reasons other than medication efficacy (e.g., due to intolerance or nonadherence).

After the screening visit procedures, patients currently being treated with IOP-lowering medication(s) in either eye will begin washout of these medication(s) for a medication-dependent minimum washout period. The maximum washout period is 42 days. Baseline visit occurs after the washout period has been completed. To be eligible to participate in the study, at the Baseline visit, patients must have an Hour 0 IOP of  $\geq 22$  and  $\leq 34$  mmHg in each eye with a difference between the eyes of  $\leq 5$  mmHg. The eye with the higher IOP at Baseline will be assigned as the primary eye. If baseline IOP is the same in both eyes, the right eye will be the primary eye. The primary eye will be randomized to receive either Bim SR or SLT using a 1:1 ratio, stratified by:

- primary eye baseline IOP ( $\leq 25$  versus  $> 25$  mmHg)

and

- 

If the primary eye receives Bim SR, the contralateral eye will receive SLT. If the primary eye receives SLT, the contralateral eye will receive Bim SR.

The study is being conducted in 2 stages because the protocol was amended ([Amendment 2](#)) to reduce the number from 3 to 2 cycles of Bim SR administration, which allows for longer duration of efficacy follow up after the second administration:

- **Stage 1:** Bim SR 15  $\mu$ g vs SLT; 3 administration cycles for patients who were enrolled and reached the Week 32 administration visit prior to implementation of Protocol Amendment 2

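### The 20% responder percentage has no stated denominator, population or rescue rule; unless all eyes stay in the denominator, rescued eyes drop out instead of counting as failures

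*SAP*

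**What the plan says.** Protocol 7.2.2 lists the percentage of eyes with at least a 20% IOP reduction as a secondary efficacy variable. SAP 10.2 gives it one sentence: the number and percent of Bimatoprost SR and SLT eyes with that "reduction in IOP by each post-baseline visit in each eye will be summarized". Protocol 7.3.2 adds nothing on denominator, population or rescue.

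The general handling of IOP after rescue is given elsewhere:

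- Protocol 7.2: measurements taken after non-study IOP-lowering medication has been started in an eye "will be included in the study database but will be excluded from efficacy analysis".
- SAP 16.1: measurements taken after such "medication or procedure in an eye will be treated as missing for that eye".

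Two other provisions show who these eyes are. Protocol 4.5.2 prohibits non-study IOP-lowering treatment "unless necessary for the safety of the patient due to inadequate control of IOP as determined by the investigator", and requires the need to be judged separately for each eye. Under Protocol 8.9, patients who received it in one or both eyes "will be followed for the duration of the study through the Week 52/Exit visit".

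**The concern.** An eye whose IOP is set to missing cannot be classed as having, or not having, a 20% reduction. If the percentage is taken over eyes with a value, a rescued eye leaves both numerator and denominator from that visit on. The plan restricts rescue to inadequate IOP control, so these eyes are not missing at random. Their status is also known, because the patients stay in follow-up and the rescue date is already needed for the Kaplan-Meier analysis.

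The table would then give response among eyes that had not yet needed rescue, not response among treated eyes. Because rescue is decided per eye, one eye of a patient can drop out while its fellow stays. The two percentages then come from different sets of patients, which weakens a paired-eye comparison. At stake is the reading of a named secondary efficacy variable.

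**Working it through.** The plan states no figure for this endpoint, so there is none to reproduce. The sample-size section concerns mean IOP change and does not bear on this point.

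**Inputs.** The documents give no rescue or responder rates for this trial, so every rate below is an assumption. The nearest figure is in Protocol 1.2.3: in the phase 1/2 study, 68% of patients were still on monotherapy with the initial implant at Month 6, so 32% were not. That is a different regimen and is used only to bound the illustration; the rescue shares below run from 10% to 30%.

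**Notation, for one treatment at one visit, with no other missing data:**

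- r = share of eyes rescued by that visit
- p = share of unrescued eyes with at least a 20% reduction; this is the observed-case percentage
- S = p × (1 − r); this is the percentage of all eyes, with rescued eyes counted as failures

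Hence p = S / (1 − r), and the observed-case rate exceeds S by p × r.

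**Case A: same true success, S = 50% in both treatments**

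| Rescue | Observed-case rates | Apparent gap |
|---|---|---|
| 10% vs 20% | 0.50/0.90 = 55.6% vs 0.50/0.80 = 62.5% | 6.9 points for the treatment with more rescue |
| 10% vs 30% | 55.6% vs 0.50/0.70 = 71.4% | 15.9 points for the treatment with more rescue |
| 15% vs 15% | 0.50/0.85 = 58.8% in both | 0 |

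**Case B: same observed-case rate p in both treatments**

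The table shows no difference. The difference in S is p × (r2 − r1), against the treatment with more rescue.

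- 10-point rescue gap: 0.50 × 10 = 5 points to 0.70 × 10 = 7 points
- 20-point rescue gap: 10 to 14 points
- p = 60%, rescue 10% vs 25%: displayed 60% vs 60%; S is 0.60 × 0.90 = 54% vs 0.60 × 0.75 = 45%
- Equal rescue of 15%: no shift between treatments, but each rate is overstated by p × 0.15, which is 7.5 points at p = 50% and 10.5 points at p = 70%

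**If the denominator is fixed at all eyes,** a blanked value is simply not counted as a response. The table then shows S directly, and none of these distortions arises.

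**Does another planned analysis cover it?** Multiple imputation and the tipping-point analysis in SAP 10.4 apply to IOP change, and the tipping region "will be used to evaluate the robustness of the noninferiority conclusion". Neither is described for responders. SAP 10.2 reports time to rescue by Kaplan-Meier, but that curve cannot be combined with an observed-case responder table to recover S at each visit unless the table also shows its denominators.

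**The case against.** **The drop-out is inferred.** A reader might take it that rescued eyes certainly leave the analysis. The documents do not say so: the denominator is unstated, and SAP 4.0 notes that "Specifications of tables, figures, and data listings (TFLs) are contained in a separate document". That document was not available, and it may fix the denominator at all eyes. Parts of the text on other efficacy analyses are also redacted, and a figure is missing beside the responder sentence, so a supplementary responder analysis cannot be ruled out. This stands. The problem is therefore conditional, but a secondary endpoint should not take two values depending on an unwritten programming choice.

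**Direction is unknown.** A reader might infer that one named treatment is flattered. No document gives rescue rates by treatment, and with equal rescue and equal response there is no shift between treatments. This stands.

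**Low consequence.** The summary has no test, alpha or success criterion, and rescue is reported in its own right. A reader might extend the point to the noninferiority or superiority conclusions; neither uses the responder percentage. This stands and limits the weight of the point.

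**Keeping response and rescue apart is defensible.** Protocol 7.2 excludes post-rescue IOP to avoid confounding. Rescue is at the investigator's discretion with no numeric threshold, and Protocol 9.4 says the primary investigator is unmasked, whereas efficacy IOP is read by masked examiners. No passage equates rescue with missing a 20% reduction. This is a real cost of counting rescue as failure, and it is why both versions should be shown. It does not justify leaving the rule unstated.

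**Conclusion.** The point holds conditionally. On the plain reading of SAP 10.2 together with SAP 16.1 and Protocol 7.2, with no failure rule and no fixed denominator, the by-visit percentage is conditional on not having been rescued. Relative to a rate that counts rescue as failure, each treatment's figure is too high by p × r.

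If rescue differs between treatments, the comparison moves in favor of the one with more rescue. With equal true success of 50%, the apparent gap is 6.9 points for 10% versus 20% rescue and 15.9 points for 10% versus 30%. These sizes rest on assumed rates, on no other missing data, and on treating rescue for inadequate control as failure. The documents do not establish that rescue will differ, or in which direction.

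The effect is confined to a descriptive secondary summary. The change is worth making because it is cheap and settles the definition of the endpoint.

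**What to change.** In SAP 10.2, and in the table specifications to match:

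1. Name the analysis population. Protocol 7.1 assigns ITT to efficacy analyses and mITT to the primary analysis; if mITT is intended here, say so.
2. Use all eyes in that population, by treatment, as the denominator at every visit.
3. Count an eye as a non-responder at every visit from its first non-study IOP-lowering treatment. State whether procedures count as well as medication: SAP 16.1 includes both, while Protocol 7.2 names medication only.
4. State how eyes with no value through discontinuation or a missed visit are counted. Restricting the denominator to patients still in the study would leave the rate conditional on staying.
5. Show the observed-case percentage alongside, with its denominator.

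SAP 16.1 should also cite Protocol 7.2 for the blanking rule; it cites Protocol 5.9.1.5, whose current text does not contain it.

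The cost is a short paragraph and one derived flag, built from the rescue date already used for the time-to-rescue analysis. This is a classification for analysis and changes no clinical rule. The downsides are lower reported rates and a composite that includes a decision made by an unmasked investigator; the observed-case version lets the reader see how much depends on that decision.
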